3.6 Post Study Drug Study Follow up

Participants who discontinue study drug must continue to be followed for collection of outcome and/or survival follow-up data as required and in line with [Section 5.1](#) until death or the conclusion of the study.

Follow-Up Visit 1 is to occur 30 days from the last dose (± 7 days), or Follow-Up Visit 1 can be performed on date of discontinuation if it is greater than 35 days from last dose. Follow-Up Visit 2 is to occur 90 days from Follow-Up Visit 1 (± 7 days). Survival Follow-Up Visits to occur approximately every 3 months from Follow-Up Visit 2. Survival Follow-up visits may be performed by phone contact or office visit.

BMS may request that survival data be collected on all participants outside of the protocol defined window ([Table 5.1-3](#)). At the time of this request, each participant will be contacted to determine their survival status unless the participant has withdrawn consent for all contact.

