Tumor Biopsy Sample:	X	
Tumor biopsy specimens will be obtained from consenting participants within all treatment arms at Week 7 and once disease progression has been documented (See Table 5.6-1). Biopsy should be excisional, incisional or core needle (fine needle aspiration is insufficient) and submitted to central lab see also Table 5.6-1

Table 5.1-2: On Treatment Procedural Outline (All Treatments) CA209651 (All Cohorts)

Procedure	During Treatment Visit ^{a,b}	Notes
Saliva Sample: Oral microbiome	X	See Table 5.6-1
Clinical Drug Supplies		
IVRS Drug Vial Assignment	X	
Dispense Study Drug	X	Within 3 days from randomization, the participant must receive the first dose of study medication.

^a For Ipilimumab/Nivolumab Arm: Visits occur every 2 weeks

^b For EXTREME regimen Arm: Visits occur every 3 weeks

Table 5.1-3: Follow-Up Period (all treatment groups)

Procedure	Follow Up, Visits 1 and 2 ^a	Survival Follow-Up Visits ^b	Notes
Safety Assessments			
Targeted Physical Examination	X		To assess for potential late emergent study drug related issues.
Vital Signs	X		
Adverse Events Assessment	X		In survival period only to include toxicities from study therapy.
Review of Concomitant Medication	X	X	Document Subsequent Cancer Therapy
Laboratory Tests	X		CBC w/ differential, LFTs, BUN or serum urea level, creatinine, Ca, Mg, Na, K, Cl, LDH, phosphate, glucose, amylase, lipase. TSH (+ reflex Free T4 and Free T3 collected ONLY if TSH is abnormal). To be done at FU1, to be repeated at FU2, if study related toxicity persists.
Pregnancy Test (WOCBP only)	X		Serum or urine.
Efficacy Assessments			
Tumor Assessment	X	X	Only for participants without progression. - Tumor assessments should occur every 6 weeks (\pm 1 week) for the first 48 weeks, then every 12 weeks (\pm 1 week) until disease progression or treatment is discontinued (whichever occurs later). - CT or MRI of the neck, chest, abdomen, pelvis and all known sites of disease. Use same imaging method as was used at screening/baseline. - MRI of the brain (without AND with Gadolinium contrast) is required for participants with a history of brain metastasis. Note: MRI of the brain is preferred but CT scan is acceptable. Surveillance scans should be performed approximately every 12 weeks, or sooner if clinically indicated. (CT of the head without AND with contrast may be performed if MRI is contraindicated).
Outcomes Research Assessment			
FACT-H&N	X		Can be collected over the phone.

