FHNSI-10		X	Can be collected over the phone.

Table 5.1-3: Follow-Up Period (all treatment groups)

Procedure	Follow Up, Visits 1 and 2 ^a	Survival Follow-Up Visits ^b	Notes
EQ-5D-3L	X	X	Can be collected over the phone.
Health care resource utilization questions	X		To be completed by the site in CRF
Participant Status			
Survival Status	X	X	Every 3 months after FU 2; may be accomplished by visit, phone contact or email, to include assessment of subsequent anti-cancer therapy

^a Follow Up visits 1 (FU1) and 2 (FU2) are in clinic visits. Follow-up visit 1 (FU1) = 30 days from the last dose ± 7 days or coincides with the date of discontinuation (± 7 days) if date of discontinuation is greater than 35 days after last dose, Follow-up visit 2 (FU2) = 90 days (± 7 days) from Follow-up Visit 1

^b Survival Follow Up Visits may be conducted in clinic or via telephone contact: Every 3 Months (± 7 days) from FU2

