On-study weight, ECOG performance status, and vital signs should be assessed at each on-study visit prior to dosing. Vital signs should also be taken as per institutional standard of care prior to, during, and after infusions. The start and stop time of the study therapy infusions should be documented.

Physical examinations are to be performed as clinically indicated. If there are any new or worsening clinically significant changes since the last exam, report changes on the appropriate non-serious or serious adverse event page.

Additional measures, including non-study required laboratory tests, should be performed as clinically indicated or to comply with local regulations. Laboratory toxicities (eg, suspected drug induced liver enzyme evaluations) will be monitored during the follow-up phase via on site/local labs until all study drug related toxicities resolve, return to baseline, or are deemed irreversible.

Some of the assessments referred to in this section may not be captured as data in the eCRF. They are intended to be used as safety monitoring by the treating physician. Additional testing or assessments may be performed as clinically necessary or where required by institutional or local regulations.

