#### • Post baseline period:

- On-treatment AEs will be defined as AEs with an onset date and time on or after the date and time of the first dose of study treatment (or with an onset date on or after the day of first dose of study treatment if time is not collected or is missing). For subjects who are off study treatment, AEs will be included if event occurred within a safety window of 100 days after the last dose of study treatment. No "subtracting rule" will be applied when an AE occurs both pre-treatment and post-treatment with the same preferred term and grade.
- On-treatment evaluations (laboratory tests, pulse oximetry and vital signs) will be defined as evaluations taken after the day (and time, if collected and not missing) of first dose of study treatment. For subjects who are off study treatment, evaluations should be within a safety window of 100 days after the last dose of study treatment.

 Late-emergent drug-related AEs will be defined as drug-related AEs with an onset date greater than 100 days after the last dose of study treatment in subjects who are off study treatment.

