# 7.6.10.1 Hematology

The following will be summarized by treatment group as worst CTC grade on-treatment per subject and as shift table of worst on-treatment CTC grade compared to baseline CTC grade per subject: hemoglobin (HB), platelets, white blood counts (WBC), absolute neutrophils count (ANC) and lymphocyte count (LYMPH).

The analyses will be conducted using the 30-day safety window.

A by-subject listing of these laboratory parameters will be provided.

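### The SAP's laboratory summaries stop at 30 days after last dose, but the only unconditional post-treatment laboratory draw may validly fall on days 31-37 or later

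*Protocol*

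**What the plan says.** **Timing of FU1.** Footnote a of Protocol Table 5.1-3 gives "Follow-up visit 1 (FU1) = 30 days from the last dose ± 7 days or coincides with the date of discontinuation". The second option, which also carries ± 7 days, applies "if date of discontinuation is greater than 35 days after last dose". Protocol 3.6 gives the same 30 ± 7 days and words the later option as permissive.

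**Laboratory tests in follow-up.** The laboratory row of Table 5.1-3 reads "To be done at FU1, to be repeated at FU2, if study related toxicity persists". FU1 is thus unconditional and FU2 is not. The timing of FU2 is "Follow-up visit 2 (FU2) = 90 days (± 7 days) from Follow-up Visit 1". Protocol 5.3 adds that laboratory toxicities "will be monitored during the follow-up phase via on site/local labs until all study drug related toxicities resolve", with no fixed days.

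**Analysis windows.** For participants off treatment, SAP 6.1 says that on-treatment "evaluations should be within a safety window of 100 days after the last dose of study treatment". SAP 7.1.2 then builds the laboratory tables on the worst on-treatment grade. SAP 7.6.10.1 says "The analyses will be conducted using the 30-day safety window", and the chemistry, electrolyte, hepatic and thyroid summaries say the same. None of the five is repeated at 100 days. SAP 6.1 does not define a 30-day window.

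**The concern.** On-treatment laboratory tests are drawn before dosing (Protocol Table 5.1-2 and 5.3). After the last dose, the first draw that the protocol requires of every participant is therefore FU1. With a 30-day limit, whether that sample counts depends on which permitted day the visit fell on: day 29 is in the table, day 33 is not, and both visits are compliant.

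At stake is the completeness of the worst-grade, shift, concurrent ALT/bilirubin and thyroid tables for the period after the last dose. The tables can also disagree with one another. Immune-mediated adverse events are summarised over 100 days (SAP 7.6.7), and their term list in Protocol 6.7.1 includes raised ALT, AST, bilirubin and creatinine. An event found at an FU1 visit on day 33 could count there while the laboratory value behind it is missing from the hepatic table.

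Elsewhere the SAP allows for a late FU1: Table 4.3.5-1 accepts FU1 questionnaires up to 76 days after last dose.

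**Working it through.** **Inputs.** FU1 on day 30 ± 7, or at discontinuation day D ± 7 when D > 35 (Protocol Table 5.1-3). FU2 at FU1 + 90 ± 7 (same table). Laboratory tables to day 30 (SAP 7.6.10.1 to 7.6.10.4). On-treatment definition to day 100 (SAP 6.1).

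**1. FU1, main rule.**
- Permitted days: 30 − 7 = 23 to 30 + 7 = 37, which is 15 days.
- Days after day 30: 31 to 37, which is 7 days; 7/15 = 46.7%.
- If day 30 itself were treated as outside the window: 8/15 = 53.3%.

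**2. FU1 tied to a later discontinuation.** Permitted days run from D − 7 to D + 7.

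| Discontinuation day D | Permitted FU1 days | After day 30 |
|---|---|---|
| 36 | 29-43 | 13/15 |
| 37 | 30-44 | 14/15 |
| 38 | 31-45 | 15/15 |

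From D = 38 onward the earliest permitted day is at least 31, so all are out.

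**3. FU2.** In the main rule the earliest day is 23 + 83 = 106 and the latest is 37 + 97 = 134. In the later branch the earliest is 29 + 83 = 112. FU2 is outside both the 30-day and the 100-day windows, so it cannot stand in for FU1 in either.

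**4. Share of main-rule visits after day 30.** The documents do not give the spread of visit days, so this is a sensitivity range. For a normal distribution with centre m and SD s, rounded to whole days and truncated to days 23-37:

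share = [Φ((37.5 − m)/s) − Φ((30.5 − m)/s)] / [Φ((37.5 − m)/s) − Φ((22.5 − m)/s)]

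| Centre m | s = 2 | s = 3 | s = 4 |
|---|---|---|---|
| 27 | 4.1% | 13.0% | 21.5% |
| 30 | 40.1% | 43.3% | 44.7% |
| 33 | 89.3% | 78.3% | 69.8% |

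A triangular distribution peaking on day 30 gives 43.8%.

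**5. With the 100-day window of SAP 6.1.** None of the 15 main-rule days is excluded. In the later branch no permitted FU1 day is excluded while D + 7 ≤ 100, that is, for discontinuation up to day 93.

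**The case against.** **The 30-day window may be deliberate.** SAP 6.1 sets the same 100-day outer limit for adverse events, yet most adverse event tables use 30 days, and SAP 7.1.1 speaks of 30 or 100 days depending on the analysis. A 30-day table inside a 100-day definition is this SAP's general pattern and applies to both arms. This stands: replacing the 30-day tables outright would be partly a matter of preference. It does not explain why the laboratory tables have no 100-day counterpart when drug-related adverse events do.

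**A reader might infer that late results are discarded.** They are not. By-subject listings are planned in each laboratory section. Laboratory results that are clinically significant, or that lead to treatment or interruption, are recorded as adverse events (Protocol 6.3). Important late abnormalities can therefore reach the 100-day tables of drug-related and immune-mediated events (SAP 7.6.5 and 7.6.7). What is missing is the value in the laboratory summaries.

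**A reader might infer that FU1 is the only later information on participants held for toxicity.** Protocol 4.5.2.1 has participants with delayed nivolumab re-evaluated at least weekly, 4.5.5.1 continues laboratory studies during long delays, and 5.3 follows toxicities by local laboratory tests. Some of these samples will fall within 30 days.

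**A reader might infer that a late-discontinuation FU1 is always lost.** The ± 7 days leave two usable days for a discontinuation on day 36 and one for day 37. The loss is complete only from day 38.

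**A reader might infer that participants who stop after one dose or cycle drop out of the tables.** The documents do not support this. Someone who attends for the next planned treatment and is then stopped has a pre-dose sample at about day 14 (Arm A) or day 21 (Arm B), inside the window. Any percentage for such participants would rest on an unsupported premise.

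**A longer window brings uneven ascertainment.** Beyond FU1 it adds mostly toxicity-driven samples. This is fair, and is a reason to add tables rather than replace them.

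**Conclusion.** The point holds as a mismatch between the visit schedule and the analysis windows. Compliant FU1 results after day 30 are omitted from all five laboratory summaries, although SAP 6.1 counts them as on-treatment up to day 100.

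The firm figures are 7 of 15 permitted days in the main rule, taking day 30 as inside the window, and every permitted day when FU1 is tied to a discontinuation on day 38 or later. The proportion of visits affected is not established: 40-45% needs visits centred on day 30 with an SD of 2 to 4 days, and moving the centre by three days either way widens the range to roughly 4-89%. How far the tables would change cannot be derived from the documents, because unscheduled samples within 30 days may already carry some of the same information.

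This concerns descriptive safety reporting. No tested endpoint is affected.

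**What to change.** In SAP 7.6.10.1 to 7.6.10.4, keep the 30-day tables for comparability and repeat the worst-grade, shift, hepatic and thyroid tables with the 100-day window of SAP 6.1, following the pattern of SAP 7.6.5. In the repeat, exclude samples taken after the start of subsequent anti-cancer therapy. Define the 30-day window in SAP 6.1 beside the 100-day one, so that the relation between them is explicit.

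The cost is SAP wording, a programming parameter and a few extra tables; no new data are needed. A footnote to the repeat should say that samples beyond FU1 are mostly toxicity-driven and that FU2 falls outside 100 days.

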5.1.1 Retesting During Screening or Lead-in Period

Retesting of laboratory parameters and/or other assessments within any single Screening or Lead-in period will be permitted (in addition to any parameters that require a confirmatory value).

Any new result will override the previous result (ie, the most current result prior to Randomization) and is the value by which study inclusion will be assessed, as it represents the participant's most current, clinical state.

Laboratory parameters and/or assessments that are included in [Table 5.1-1](#), Screening Procedural Outline may be repeated in an effort to find all possible well-qualified participants. Consultation with the Medical Monitor may be needed to identify whether repeat testing of any particular parameter is clinically relevant.

5.2 Study Materials

- NCI CTCAE version 4
- Nivolumab Investigator Brochure
- Ipilimumab Investigator Brochure
- Pharmacy Binder
- Laboratory manuals for collection and handling of blood (including PK, biomarker and immunogenicity) and tissue specimens
- Site manual for operation of Interactive Voice Response System (IVRS), including enrollment worksheets
- Manual for entry of local laboratory data
- Pregnancy Surveillance Forms
- RECIST 1.1 pocket guide
- Study Imaging Manual

5.3 Safety Assessments

At baseline, a medical history will be obtained to capture relevant underlying conditions. The baseline examinations should include weight, height, ECOG Performance Status, blood pressure (BP), heart rate (HR), and temperature at rest and should be performed within 28 days prior to first dose. Baseline signs and symptoms are those that are assessed within 14 days prior to first dose. Concomitant medications will be collected from within 14 days prior to the first dose through the study treatment period (see [Section 5.1](#)).

Baseline local laboratory assessments should be done within 14 days prior to randomization and are to include: CBC w/differential, LFTs (ALT, AST, total bilirubin, alkaline phosphatase), BUN or serum urea level, creatinine, albumin, Ca, Mg, Na, K, Cl, phosphate, LDH, glucose, amylase, lipase, Thyroid function tests includes TSH, free T4, and free T3.

The following baseline local laboratory assessments should be done within 28 days prior to first treatment: Hepatitis B and C testing (HBV sAg and HCV Ab or HCV RNA).

Pregnancy testing for WOCBP (done locally) must be performed within 24 hours prior to the Day 1 of first dose and then every 4 weeks \pm 1 week regardless of dosing cycle

For Arm A: local laboratory assessments should be done within 72 hours prior to each dose.

For Arm B: to be performed within 72 hours prior to dosing of Day 1 of each Cycle, every cycle (3 weeks) or more frequently as clinically indicated for weekly cetuximab dosing visits, including CBC w/differential, (Albumin if clinically indicated), LFTs (ALT, AST, total bilirubin, alkaline phosphatase), BUN or serum urea level, creatinine, Ca, Mg, Na, K, Cl, LDH, phosphate, glucose, amylase, lipase, TSH with reflexive Free T4, Free T3 (Thyroid Function Testing to be evaluated every 6 weeks). Free T4 and Free T3 assessment will be done only if TSH is abnormal

Participants will be evaluated for safety if they have received any study drug. Toxicity assessments will be continuous during the treatment phase. During the safety follow-up phase (Table 5.1-3), toxicity assessments should be done in person. Once participants reach the survival follow-up phase either in person or documented telephone calls to assess the participant's status are acceptable.

Adverse events and laboratory values will be graded according to the NCI-CTCAE version 4.0.

On-study weight, ECOG performance status, and vital signs should be assessed at each on-study visit prior to dosing. Vital signs should also be taken as per institutional standard of care prior to, during, and after infusions. The start and stop time of the study therapy infusions should be documented.

Physical examinations are to be performed as clinically indicated. If there are any new or worsening clinically significant changes since the last exam, report changes on the appropriate non-serious or serious adverse event page.

Additional measures, including non-study required laboratory tests, should be performed as clinically indicated or to comply with local regulations. Laboratory toxicities (eg, suspected drug induced liver enzyme evaluations) will be monitored during the follow-up phase via on site/local labs until all study drug related toxicities resolve, return to baseline, or are deemed irreversible.

Some of the assessments referred to in this section may not be captured as data in the eCRF. They are intended to be used as safety monitoring by the treating physician. Additional testing or assessments may be performed as clinically necessary or where required by institutional or local regulations.

5.3.1 ECOG Performance Status

Eastern Cooperative Oncology Group (ECOG) Performance Status will be evaluated and documented at Screening and within 72 hours prior to each dosing visit as outlined in Section 5.1. See Appendix 1 for description of ECOG status.

5.3.2 Pregnancy Testing

WOCBP are required to have pregnancy tests performed. WOCBP must exhibit a negative serum or urine pregnancy (minimum sensitivity 25 IU/L or equivalent units) of HCG within 24 hours prior to Day 1 of first dose and then every 4 weeks (\pm 1 week) during the treatment period and first

2 follow-up visits. Pregnancy testing will be done locally and as outlined in [Section 5.1](#). An extension up to 72 hours prior to start of study drug may be permissible in situations where results cannot be obtained within the standard 24 hour window. This is participant to medical monitor approval.

5.3.3 Thyroid Function Testing

Local thyroid function testing will be performed as outlined in Section 5.1.

At Screening, thyroid function testing is to include TSH, free T3 and free T4. At subsequent time points, thyroid function testing consists of TSH only. However, if the TSH is abnormal, reflexive testing of free T3 and free T4 are to be performed.

Management algorithms for suspected endocrinopathy adverse events (including abnormal thyroid function) can be found in the nivolumab investigator brochure and [Appendix 2](#) of the protocol.

5.3.4 Electrocardiogram (ECG)

All participants who have met the eligibility criteria are required to have a 12-lead ECG performed during Screening. If clinically indicated, additional ECGs may be obtained during the study.

5.4 Efficacy Assessments

Study radiologic tumor evaluations will take place in accordance with Time and Events tables in Section 5.1 and according to RECIST 1.1 [Appendix 3](#).

Sites will be trained prior to scanning the first study participant. Image acquisition guidelines and submission process will be outlined in the study Imaging Manual to be provided by the radiology vendor. Images will be submitted to an imaging third-party radiology vendor for central review as they are performed on an ongoing basis.

Screening (baseline) tumor assessments are to be performed prior to first dose. In addition to the brain/head, neck, chest, abdomen, pelvis, all known sites of disease should be assessed at baseline. Subsequent assessments should include brain (only if brain metastases are detected at screening, or if clinically indicated during the course of the trial), neck, chest, abdomen, pelvis, and all known / suspected sites of disease using the same imaging method and technique as was used at baseline.

A Screening MRI of the brain without and with Gadolinium contrast, including base of skull involvement, is preferred but CT scan is acceptable for all participants, in order to rule out active metastases. A CT of the head (with and without contrast) to be performed if MRI is contraindicated or unavailable.

Radiographic tumor response will be assessed at Week 6 (± 1 week) from first dose date, then every 6 weeks (± 1 week) for the first 12 months (until week 48) and every 12 weeks (± 1 week) thereafter, until disease progression is documented or treatment is discontinued (whichever occurs later). Previously treated CNS metastases are not considered measurable lesions for purposes of RECIST determined response. MRI of the brain (without AND with Gadolinium contrast) is required for participants with a history of brain metastasis. Surveillance scans should be performed approximately every 12 weeks, or sooner if clinically indicated (CT of the head without AND with contrast may be performed if MRI is contraindicated).

CT with PO and IV contrast or contrast-enhanced MRI are the preferred imaging modalities for assessing radiographic tumor response. If a participant has a known allergy to contrast material, local prophylaxis standards may be used to obtain the assessment with contrast if at all possible, or use the alternate modality. In cases where contrast is strictly contraindicated, a non-contrast scan will suffice. Should a participant have a contraindication for CT IV contrast, contrast-enhanced MRI of the head, neck, chest, abdomen and pelvis may be obtained. Every attempt should be made to image each participant using the same image modality, acquisition protocol, and same scanner for all imaging time points.

Use of CT component of a PET/CT scanner: Combined modality scanning such as with FDG-PET/CT is increasingly used in clinical care, and is a modality/technology that is in rapid evolution; therefore, the recommendations outlined here may change rather quickly with time. At present, low dose or attenuation correction CT portions of a combined FDG-PET/CT are of limited use in anatomically based efficacy assessments, and it is therefore suggested that they should not be substituted for dedicated diagnostic contrast enhanced CT scans for anatomically based RECIST measurements. However, if a site can document that the CT performed as part of a FDG-PET/CT is of identical diagnostic quality to a diagnostic CT (with IV and oral contrast) then the CT portion of the FDG-PET/CT can be used for RECIST 1.1 measurements. Note, however, that the FDG-PET portion of the CT introduces additional data which may bias an investigator if it is not routinely or serially performed.

Bone scan or PET scan is not adequate for assessment of RECIST 1.1 response in target lesions. In selected circumstances where such modalities are the sole modality used to assess certain non-target organs, those non-target organs may be evaluated less frequently. For example, bone scans may need to be repeated only when complete response is identified in target disease or when progression in bone is suspected.

Tumor assessments for all participants should continue as per protocol even if dosing is delayed or discontinued. Tumor measurements should be made by the same investigator or radiologist for each assessment whenever possible. Change in tumor measurements and tumor response to guide ongoing study treatment decisions will be assessed by the Investigator using the RECIST 1.1 criteria ([Appendix 3](#)).

All radiographic assessments performed for study purposes will be submitted to the third-party radiology vendor for central review. Tumor assessments should be submitted to the third-party radiology vendor as they are performed on an ongoing basis.

At the time of investigator-assessed off-treatment disease progression, the site must complete the tumor assessment pages in TAO documenting disease progression and submit a fresh biopsy sample of metastatic site to Central Lab for biomarker analysis as specified in [Section 5.6.3](#).

In addition, participants receiving nivolumab and ipilimumab treatment beyond progression must continue tumor assessments until such treatment has been discontinued.

Refer to the study Imaging Manual for further guidance on obtaining and submitting study related scans.

